#### 4.2.3 **Rationale for Endpoints**

#### 4.2.3.1 Safety and Efficacy Endpoints

Safety and efficacy are the primary endpoints for this study. Safety is an important endpoint for a study like this for a number of factors. First of all, the inflammatory events surrounding chemoradiation, while potentially allowing for improved immune clearance with pembrolizumab, may end up causing more toxicity. The PD-1: PD-L1 pathway is important in normal, healthy individuals in protecting from autoimmunity during inflammatory events. As CRT will induce an inflammatory event in the head and neck region, one can surmise that PD-L1 and PD-1 upregulation may be a normal response meant to protect from autoimmune events. Evaluation of safety during and following this period is paramount to understanding the role of PD-1 inhibitors combined with CRT. While a certain level of toxicity is expected with this combination, special attention will be paid to immune-related toxicities and exacerbation of known CRT related toxicities. If this combination is not felt to be safe, it would not be recommended to move forth with further evaluation.

Efficacy is the co-primary endpoint for the study. This endpoint is important to estimate the clinical benefit of this combination. If there is little to no added benefit with this combination, it would not be recommended to move forth with additional studies utilizing this combination. If the treatment is efficacious, it would be reasonable to consider phase III testing of this combination, comparing it to high-dose bolus cisplatin.

Complete response rate was chosen as the primary efficacy measure. While progression-free survival may be a reasonable alternative to this efficacy measure, complete response rate was chosen based on several factors. First, this was the efficacy measure in preclinical studies that suggested this combination was efficacious. Second, this outcome can be compared to the Intergroup Trial [13], which evaluated high-dose bolus cisplatin in a phase III setting. In this study, imaging and clinical response were used to determine response rate. The complete response rate in those treated with high-dose bolus cisplatin was 40.2% among 87 analyzable patients. While the imaging and response criteria from that study does not directly match what

is proposed in this study, we feel the response criteria documented is stricter and mirrors what is done in standard clinical practice today, to follow response in patients treated with CRT. This endpoint is supported by the fact that patients without a CR will have salvage surgery. This will give a true pathologic response. A second analysis looking at pathologic and radiographic response will be performed. This will give a second assessment of efficacy of this combination. The main purpose for using response as an assessment is for rapid analysis of the efficacy of this regimen. Due to the nature of head and neck cancer treatment and the interest in improving therapy, it is important to rapidly estimate efficacy and move forward with phase III testing if signals are present.

Although they are not primary endpoints, important survival and response endpoints will be followed as secondary endpoints during this study. These will include progression-free survival, overall survival, locoregional control (LRC) rate, distant metastasis (DM) rate, and overall response rate (ORR). While the study is not powered for these endpoints, they will be compared to historical data from similar head and neck studies. If these are found to be superior to historical data and the analysis is statistically sound, these endpoints may be considered when deciding whether to move forward with further evaluation of this combination. As these data points take longer to mature, we have opted to have them serve as secondary endpoints and keep CR rate as the primary measure of efficacy.

#### 4.2.3.2 Pharmacokinetic, Biomarker, and Patient Report Outcomes Research

There are ongoing clinical trials evaluating pembrolizumab in combination with platinumdoublet therapy in non-small cell lung cancer and in other chemotherapy combination studies [31]. This will be the first study looking at pembrolizumab in combination with weekly cisplatin chemotherapy. Despite this, based on data from other combination studies, the risk for a drug-drug interaction is extremely low. Furthermore, pembrolizumab has been utilized with cisplatin at varying doses in a number of studies with accompanying pharmacokinetic data. As a result, pharmacokinetic data will not be obtained during this study. Additionally, as it is felt there is reasonable data available to understand the risk of anti-drug antibodies with this combination. Therefore, this will also be excluded from this protocol.

PD-L1 expression may be an important factor in efficacy. Current data supports high PD-L1 expression as a correlate of response to therapy. While patients with no or low expression may still respond to pembrolizumab, the response rates are significantly higher for those with high expression. As we venture into multimodality therapy with chemotherapy and radiation, it will be important to see if baseline expression of PD-L1 correlates with a response. As previously mentioned, data is emerging that suggests altered PD-L1 expression during both chemotherapy and radiation. While we will not be performing biopsies during therapy, the baseline PD-L1 expression may be important to see if this biomarker maintains its predictive nature in the setting of chemoradiation. There is the potential that the biomarker will not continue to predict response, as even non-expressers or low expressers at baseline, may develop enhanced responses during CRT. It will be important to evaluate PD-L1 expression to generate hypotheses for future biomarker research.

A final supportive outcome of importance is patient-related outcomes (PRO). High-dose bolus cisplatin is highly toxic and leads to severe acute and late effects for patients. Survivors of head and neck cancer experience some of the most severe late effects from therapy [32]. During treatment, the majority of patients will require feeding tubes as they will develop severe mucositis, dysphagia/odynophagia, nausea/vomiting, loss of appetite, xerostomia/sialorrhea, and malnutrition [12]. Fatigue, difficulties with speech, and inability to eat can affect mood. It may take anywhere from 12-36 months for most patients to return back to an acceptable baseline quality of life (QOL) [33]. Some patients will never return to a self-rated acceptable QOL. The factors degrading QOL are complex, but include psychosocial symptoms and chronic somatic changes related to the disease and associated treatment [34]. Many feel that low-dose weekly cisplatin may be better tolerated and have improved QOL indices [17]. We feel that QOL is an extremely important endpoint to evaluate when developing a novel combination as proposed. This is important, as even if efficacy is improved, if QOL is significantly degraded, it may not be worthwhile to move forward with further testing. Fortunately, we have QOL data, using the Functional Assessment of Cancer Therapy Head and Neck (FACT H&N) survey, from approximately 50 patients treated with standard of care, highdose bolus cisplatin in this setting for comparison at approximate time points as outlined in this study [35]. We propose using the same OOL survey for this study. While it is not a head to head comparison in a randomized trial, it does provide insight into how this combination may be tolerated in a phase III comparison to standard therapy.

## 4.2.3.3 Exploratory Research

As previously mentioned, we have data from a randomized phase 2 trial in this setting, in this same patient population [35]. The study utilized high-dose bolus cisplatin 100 mg/m2 on days 1, 22, and 43 with or without the agent dichloroacetate (DCA). From this study, we have historically banked specimens from 40-50 patients undergoing primary CRT. These specimens include tumor RNA/DNA (freshly isolated), tumor blocks of primary and metastatic nodal specimens, peripheral immune cells isolated to remain live and functional. Quality of life analyses, response data, and survival data were also prospectively collected and can be correlated to outcomes. These data will be used as a control to ascertain changes seen with the addition of PD-1 inhibition as proposed in this study. This data, combined with the correlative studies performed during this study, can provide valuable insight into biomarkers for treatment response, targets for future therapy, and other potential factors that may impact efficacy and safety, as we enter the field of chemoimmunoradiotherapy.

While this is still developing in this field, several of the key areas of exploratory research in this setting include: circulating immune cell analysis, tumor infiltrate immune cell analysis, the HPV specific immune response [11], and tumor genomic alterations [36]. We have the capability to collect specimens and evaluate each of these factors during and following CRT. As previously mentioned, we have experience with these procedures from a prior study in a similar population. Furthermore, our cancer biology COBRE grant funding and core facilities will help fund and assist in this testing.

# 4.2.3.4 Exploratory Molecular Profiling and Analysis and its Rationale

Genomic sequencing of tumor cells from tissue relative to non-tumor cells from whole blood will be profiled to identify the genomic variances that may contribute to response or disease progression and provide an understanding of molecular abnormalities. RNA sequencing will be conducted to provide expression data and give relevance to DNA mutations; Quantitative proteomics analysis will be conducted to determine the exact amounts of specific proteins and to confirm expression of genes that are correlative of response and disease progression. Flow cytometry and T-cell gene analysis utilizing similar techniques will be utilized to evaluate peripheral blood immunocyte response during therapy. All genomic, transcriptomic, and proteomic molecular analyses will be retrospective and exploratory.

## 4.2.3.5 **Preliminary Results and Rationale for Expansion Cohort**

The current study has enrolled 27 patients from November 18, 2015 to August 6, 2016. The study is currently on hold for an interim safety and efficacy analysis. As of the data lock on September 14, 2016, 20 (74.1%) patients with HPV positive (p16 positive) disease and 7 (15.9%) with HPV negative (p16 negative) disease have enrolled. Early response data in imaged patients (n=9), shows a CR (CT and/or PET or pathologic CR on salvage surgery) in 8/8 (100%) of HPV positive patients and a PR in the single HPV negative patient. We anticipate easily hitting our primary endpoint of CR rate >60% in our HPV positive population based on these early results. However, based on our lack of HPV negative patients, it is unclear what responses will be seen.

Recent data analysis of an internal study (NCT01386632) using standard of care high-dose cisplatin (100 mg/m2 on days 1, 22, and 43) in a similar cohort of patients was performed. Distinct differences in response were seen in the HPV+ and HPV- groups, which mirror efficacy findings in similar studies. This analysis has revealed that 20 of 27 (74%) of evaluable patients with HPV positive disease achieved a CR (based on 3-month post-radiation CT and/or PET or subsequent salvage surgery). In the same study, the evaluable patients in the HPV negative cohort had 6 of 12 (50%) achieving the same CR endpoint.

Due to the historically good responses in HPV positive disease and the early findings in our current HPV positive cohort, we propose evaluation of efficacy separately in the HPV positive and HPV negative cohorts. As a result, we propose adding expansion cohorts after the interim analysis to explore efficacy in each of these unique populations. Addition of both HPV negative and HPV positive patients will provide further insight into efficacy of this novel combination.

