Based on this new data, we have reassessed our power calculations for our HPV positive cohort, With this novel combination therapy we estimate that an improvement in efficacy of >20% to a CR rate of 90% would warrant future study of this regimen in HPV positive disease. Therefore, using a one-arm binomial design the null hypothesis that the true response rate is 74% will be tested against a one-sided alternative. The null hypothesis will be rejected if 31 or more CRs are observed in 34 patients. This design yields a type I error rate of 0.05 and power of 80% when the true response rate is 90%.

Reviewing the same data, the HPV negative cohort had 6 of 12 (50%) evaluable patients achieving a CR (based on 3-month post-radiation CT and/or PET or subsequent salvage surgery). Therefore, reassessing our power calculations for the HPV negative cohort in the proposed expansion cohort, we estimate a CR rate of 75% (50% improvement from the standard of care) with the study regimen would warrant future study of this regimen in HPV negative disease. Therefore, using a one-arm binomial sample size, the null hypothesis with a true response rate of 50% will be tested against a one-sided alternative. The null hypothesis will be rejected if 18 or more responses are observed in 23 patients. This design yields a type I error rate of 0.05 and power of 80% when the true response rate is 75%.

At the time of the interim analysis, 20 patients with HPV + disease are enrolled and 7 patients with HPV - disease are enrolled. Based on this reanalysis of sample size and power calculations, an additional 14 HPV positive patients and 16 HPV negative patients would need to be enrolled after the interim analysis.

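### The HPV+ test was set after 8/8 complete responses were known and counts those patients, and its single stated error of 0.05 matches neither 1.2% (all outcomes unseen) nor 6.5% (conditional on 8/8)

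*Combined protocol and SAP*

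**What the plan says.** Section 4.2.3.5 gives the state of the trial at the 14 September 2016 lock: 27 patients enrolled, 20 of them HPV+, and nine imaged. CRs were seen "in 8/8 (100%) of HPV positive patients and a PR in the single HPV negative patient". The section then justifies the separate HPV cohorts by historically good HPV+ responses and by this trial's own results: "the early findings in our current HPV positive cohort, we propose evaluation of efficacy separately in the HPV positive and HPV negative cohorts".

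The new HPV+ null comes from an internal high-dose cisplatin study: "This analysis has revealed that 20 of 27 (74%) of evaluable patients with HPV positive disease achieved a CR". Section 8.4.7.3 builds the test on it: "using a one-arm binomial design the null hypothesis that the true response rate is 74% will be tested against a one-sided alternative". The target is that "an improvement in efficacy of >20% to a CR rate of 90% would warrant future study of this regimen in HPV positive disease". The rule is "The null hypothesis will be rejected if 31 or more CRs are observed in 34 patients", and its stated properties are "This design yields a type I error rate of 0.05 and power of 80% when the true response rate is 90" per cent.

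Patients already enrolled count toward the cohort sizes: "an additional 14 HPV positive patients and 16 HPV negative patients would need to be enrolled after the interim analysis". Since 20 + 14 = 34, the 8 known responders are among the 34. Section 8.4.7.2 plans no multiplicity adjustment. The plan contains no analysis that separates patients whose response was known at the redesign from the rest.

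**The concern.** Results from this trial helped to prompt a separate HPV+ hypothesis, and the same results count toward passing it. The quoted type I error treats all 34 outcomes as unseen when the rule was set. A reader told that 31 of 34 responded and 74% was rejected at the 5% level could not tell that 8 of the 31 successes may have preceded the rule. Because section 8.4.7.3 uses the result to judge whether the regimen merits further study in HPV+ disease, the error should be stated on a basis the reader can interpret.

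**Working it through.** **Inputs.** Null 0.74, alternative 0.90, cut-off 31 of 34, stated error 0.05 and power 80% (section 8.4.7.3); 8 CRs in 8 imaged HPV+ patients (section 4.2.3.5). Write P(n, r, p) for the exact binomial probability of at least r successes in n at rate p.

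**1. The plan's own figures.**
- P(34, 31, 0.74) = 0.0122 and P(34, 31, 0.90) = 0.554. The rule as written has 1.2% error and 55% power, so the stated 0.05 and 80% do not reproduce.
- The sample size does follow from the arcsine formula: (1.645 + 0.842)² / (2·asin√0.90 − 2·asin√0.74)² = 33.97.
- At 30 of 34 the exact error is 3.75% and the power 75%.

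**2. Conditional on 8/8.** Success needs 31 − 8 = 23 CRs among 34 − 8 = 26 patients. P(26, 23, 0.74) = 0.0649, or 6.5%. With 20/27 as the null it is 6.6%.

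**3. Consistency with the unconditional error.** Split the 1.2% by the number of CRs in the first eight, under the null:

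| CRs in first 8 | Probability | Needed in other 26 | Chance of success | Product |
|---|---|---|---|---|
| 8 | 0.0899 | 23 | 0.0649 | 0.0058 |
| 7 | 0.2527 | 24 | 0.0200 | 0.0051 |
| 6 | 0.3108 | 25 | 0.0040 | 0.0013 |
| 5 | 0.2184 | 26 | 0.0004 | 0.0001 |

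The products add to 0.012, so the 6.5% and the 1.2% describe the same rule.

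**4. How far the 6.5% depends on assumptions.**
- Rule also written after 7/8: (0.0899 × 0.0649 + 0.2527 × 0.0200) / (0.0899 + 0.2527) = 0.032.
- Central review reverses one of the eight CRs: 24 of 26 are needed, P(26, 24, 0.74) = 0.020.
- Cut-off 30 instead of 31: given 8/8, P(26, 22, 0.74) = 0.156.

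The last case matters because Table 7 (section 8.4.3.2) assigns the CR rate an asymptotic one-sided test. Applied to the HPV+ cohort at 74%, 30 of 34 gives z = (0.8824 − 0.74)/√(0.74 × 0.26/34) = 1.89, p = 0.029, which rejects. The text of section 8.4.3.1 still describes that test for all subjects against 40.2%, so the plan does not say which rule governs the HPV+ cohort.

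**5. Number known when the rule was set.** Section 4.2.3.5 has nine patients imaged, whereas section 8.4.7.1 places the interim after all 27 have treatment-end assessments. As an illustration, suppose all 20 enrolled HPV+ outcomes were known. With 17, 18 or 19 CRs, success would need 14, 13 or 12 of the remaining 14, and the conditional error would be 1.5%, 8.7% or 25.3%.

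**6. The estimate.** At a true 74%, and given 8/8, the expected observed rate is (8 + 26 × 0.74)/34 = 27.24/34 = 80.1%, which is 6.1 points high.

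**7. Test on the unknown outcomes, if these are 26.** At a cut-off of 24 the error is 2.0% and the power P(26, 24, 0.90) = 51%. At 23 the error is 6.5%, so 24 is the lowest cut-off with error below 5%.

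**The case against.** A reader might infer that the real chance of a false HPV+ success is 6.5%, in breach of the stated 5%. The documents do not support that. Any fixed rule has a higher conditional error after a good start, and 8/8 is the best possible start. Over all paths the error is 1.2%, and under the null the probability of both 8/8 and success is only 0.6%. The 6.5% also assumes that the rule would have been written only after 8/8, and the plan does not say which early results would have led to it.

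Nor was the threshold loosened to fit good data. The 74% comes from another study. The earlier all-comers test had a null of 40.2% and rejected at 21 of 39 (54%); the HPV+ test now needs 31 of 34 (91%). Historical responses are named ahead of the trial's own findings as the reason for the split. Response was assessed by sites, with central radiology review due at the end of the study (section 7.1.2.6.2), so the eight CRs may not be final. This is a Phase IB expansion meant to explore efficacy, and the redesign and early data are disclosed.

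All of this stands, and it limits the size and severity of the point. It does not remove it: the trial's own responses are cited as a reason for the separate test, the same patients count toward it, and the quoted error takes no account of this.

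**Conclusion.** The point holds at moderate severity. The single 0.05 in section 8.4.7.3 should not stand alone: the 31/34 rule has an exact error of 1.2% with all outcomes unseen and 6.5% conditional on 8/8. Under the other assumptions examined for 31/34 with eight outcomes known, the figure is 3.2% or 2.0%. It is 15.6% given 8/8 if 30 of 34 suffices. The 6.5% rests on exactly eight HPV+ outcomes being known when the rule was set, on all eight standing as CRs, and on the rule being written only after 8/8. The documents do not date the rule, so the split into 8 known and 26 unknown is an assumption.

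The mismatch between the stated 5% and 80% and the exact 1.2% and 55% is a separate error. Correcting it by moving the cut-off to 30 would enlarge the present problem.

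**What to change.** In section 8.4.7.3, replace the single 0.05 with two figures: the unconditional error (1.2% for 31/34) and the error conditional on the responses known when the rule was set. State how many were known and on what date (8 at the 14 September 2016 lock, if that is the date). Say whether the count of 31 or the Table 7 test governs the HPV+ cohort.

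In section 8.4.3.1, keep all 34 patients for the main HPV+ analysis. Pre-specify a sensitivity analysis in HPV+ patients whose treatment-end response was unknown at that date: CR rate, exact confidence interval, and exact test against 74%. If these are 26 patients, the cut-off is 24, with error 2.0% and power 51% at a true 90%. Report both results with any claim that 74% was rejected, and disclose that the all-34 estimate includes patients whose responses helped prompt the hypothesis.

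The cost is wording and one extra analysis of modest power, with no new patients. Basing the claim on the 26-patient test alone is not required. Given 8/8 it amounts to asking for 32 of 34, and its 51% power compares with 75% for a 30/34 cut-off.

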## **5.0 METHODOLOGY**

#### 5.1 Entry Criteria

#### 5.1.1 **Diagnosis/Condition for Entry into the Trial**

Male and female patients with TNM clinical stage III, IVA, or IVB squamous cell carcinoma of oral cavity (excluding lip), oropharynx, hypopharynx, and larynx eligible for curative-intent treatment. A total of 57 patients will be enrolled with 34 of those patients being HPV-positive and 23 patients being HPV-negative. Enrollment to each sub-category will end when the target is met.

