#### 5.10 Subject Replacement Strategy

A subject who discontinues from the trial during the active treatment for reasons other than AE/SAE or progression will be replaced.

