is estimated that57 evaluable patients, will be	Sample Size and Power	Sample size is based off the efficacy endpoint. It
	1	
		sufficient to determine the efficacy endpoint
with a power $= 0.8$ and one-sided alpha $= .05$ .		

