#### 8.4.2.1 Analysis Populations

#### 8.4.2.2 Efficacy Analysis Populations

The Full Analysis Set (FAS) population will serve as the primary population for the analysis of efficacy data in this study. The FAS population consists of all subjects who:

- Receive at least one dose of study treatment,
- Complete the treatment end imaging study

A supportive analysis using the All Patients as Treated (APaT) population, defined as all enrolled subjects who receive at least one dose of study medication, will be performed for the primary efficacy endpoint(s). Supportive analyses in the FAS population using the site radiology assessment will require baseline scan with measureable disease per RECIST 1.1 using site radiology assessment.

Patients who undergo surgical resection prior to treatment end imaging will be included in the efficacy analysis. These patients will be determined as having PD.

Details on the approach to handling missing data are provided in Section 8.6 Statistical Methods.

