#### 8.4.7.1 Interim Efficacy Analysis

An interim analysis will also occur to evaluate efficacy. The interim analysis will occur after 27 patients are accrued to the study and have treatment end response assessments completed (imaging and if applicable, salvage surgical resection). This will occur at approximately 9 months after study initiation. In terms of efficacy, futility will be determined if 13 or fewer CRs (rCR +pCR) are seen in the 27 patients. If futility is not determined, the study will continue to accrue to final total of 34 HPV + patients and 23 HPV - patients who are evaluable for treatment response. This will be presented to and evaluated by the DSMB.

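### The cohort sizes 34 and 23 are called enrolled in some sections and evaluable in others, and the success rule is given only as counts at exactly those sizes

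*Combined protocol and SAP*

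**What the plan says.** **Enrolled.** Section 5.1.1 reads "A total of 57 patients will be enrolled with 34 of those patients being HPV-positive and 23 patients being HPV-negative", followed by "Enrollment to each sub-category will end when the target is met". Sections 1.0, 2.1 and 5.5 also give 34 and 23 as enrolled or total subjects.

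**Evaluable.** Section 8.4.7.1 says that, if the interim is not futile, "the study will continue to accrue to final total of 34 HPV + patients and 23 HPV - patients who are evaluable" for response. The summary in section 8.1 likewise speaks of 57 evaluable patients.

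**Accrual still needed.** Section 8.4.7.3 adds 14 HPV-positive and 16 HPV-negative patients to the 20 and 7 already enrolled.

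**Replacement.** Section 5.10: "A subject who discontinues from the trial during the active treatment for reasons other than AE/SAE or progression will be replaced".

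**Efficacy set.** Under section 8.4.2.2 a patient must be treated and must also "Complete the treatment end imaging study". Patients resected before that scan stay in as progressive disease. Table 7 counts missing data for the CR rate as non-response.

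**Success rule.** For the HPV-positive cohort, section 8.4.7.3 states "The null hypothesis will be rejected if 31 or more CRs are observed in 34 patients", against a null of 74% and with 90% as the alternative. The HPV-negative rule is 18 of 23, against 50% with 75% as the alternative. Each is said to have type I error 0.05 and power 80%. The test described in section 8.4.3.1 is a one-sided asymptotic test on all subjects against 40.2%, with the 21-response cut-off of the superseded 39-patient design.

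**The concern.** A site working from section 5.1.1 closes a cohort at the 34th or 23rd enrolment. A statistician working from section 8.4.7.1 expects that many patients with a response assessment. The two agree only if nobody is lost before the day-150 scan. Section 5.10 does not replace patients who leave because of adverse events or progression, nor those lost after active treatment but before imaging.

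A count tied to one n does not carry over to another. With fewer patients analysed, the same count is a higher required proportion and power falls. With more, the type I error rises. At stake is the decision rule for the co-primary efficacy endpoint in each cohort. If it is left open, the cut-off for the actual n would be chosen after the responses are known, in an open-label single-arm trial.

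**Working it through.** **Inputs.** From section 8.4.7.3: N = 34, p0 = 0.74, p1 = 0.90, count 31; and N = 23, p0 = 0.50, p1 = 0.75, count 18. The loss rate d is an assumption, because the documents give none.

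**Formula.** For a rule of r or more responses in n, P(success) = Σ from k = r to n of C(n,k) p^k (1−p)^(n−k). Setting p = p0 gives the type I error and p = p1 the power.

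**Step 1: accrual arithmetic.** 20 + 14 = 34 and 7 + 16 = 23. Every enrolled patient is counted as evaluable.

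**Step 2: the plan's own rules at full n.** 31 of 34 has type I error 0.0122 and power 0.554. 18 of 23 has 0.0053 and 0.468. Neither reproduces 0.05 and 80%. The smallest counts with type I error at most 0.05 are 30 of 34 (0.0375, power 0.750) and 16 of 23 (0.0466, power 0.804). That mismatch is a separate matter, so the effect of a changed n is measured below with 30 and 16.

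**Step 3: power as n falls.**

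| HPV-positive n | 31 fixed | 30 fixed | exact cut-off at n | power |
|---|---|---|---|---|
| 34 | 55% | 75% | 30 | 75% |
| 33 | 35% | 58% | 29 | 77% |
| 32 | 16% | 37% | 29 | 60% |
| 31 | 4% | 17% | 28 | 62% |

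| HPV-negative n | 18 fixed | 16 fixed | exact cut-off at n | power |
|---|---|---|---|---|
| 23 | 47% | 80% | 16 | 80% |
| 22 | 32% | 70% | 16 | 70% |
| 21 | 19% | 57% | 15 | 74% |
| 20 | 9% | 41% | 15 | 62% |

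**Step 4: average over random loss.** The number analysed is taken as Binomial(N, 1−d), and power is averaged over it. At d = 5%, HPV-positive power is 44% with 30 held fixed and 69% with the cut-off set at the realised n. HPV-negative power is 67% with 16 held fixed and 73% with the realised-n cut-off.

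**Step 5: when the stated counts cannot be met.** 31 responses are out of reach at n ≤ 30, that is after 34 − 30 = 4 losses. 18 are out of reach at n ≤ 17, after 23 − 17 = 6 losses. At d = 5%, P(4 or more of 34) = 8.8% and P(6 or more of 23) = 0.08%. At d = 10% they are 45% and 2.3%.

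**Step 6: the asymptotic test at other n.** Its cut-offs can be lower than the exact ones: 28 of 32, 27 of 31, 15 of 22 and 14 of 20, with exact type I error of 5.5%, 6.6%, 6.7% and 5.8%.

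**The case against.** A reader might infer that the plan stops at 34 and 23 enrolled, so that losses make success impossible. The documents do not support that as a statement of fact:

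- Section 8.4.7.1 accrues to evaluable patients, section 2.1 says approximately 57, and section 5.10 replaces some losses. Closing at enrolled is one of two documented readings.
- Impossibility needs at least 4 HPV-positive or 6 HPV-negative losses, with the counts applied mechanically. No section says they would be.
- Stopping treatment is not missing the scan. Sections 5.9 and 7.1.5.5 keep patients who stop for reasons other than progression in disease follow-up, and flow-chart note 17 urges those who stop pembrolizumab to return at day 150. The size of the loss is unknown.
- Comparing the stated counts with realised-n cut-offs (25% against 69%, and 31% against 73%, at 5% loss) would overstate this point, because most of the HPV-negative gap and part of the HPV-positive one come from 31 and 18 themselves.

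These objections stand and limit the claim. Two others stand only in part. A one-sample test can be run at any n, but the narrative in section 8.4.3.1 ties it to the pooled 40.2% null, and step 6 shows that it can exceed 5%. If missing scans count as failures over all 34 and 23, n does not shrink and a fixed count is coherent and conservative. However, the scan requirement in section 8.4.2.2 removes those patients before that rule can act, so the plan does not say which denominator holds.

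**Conclusion.** The contradiction between enrolled and evaluable is certain from the text. So is the lack of any stated cohort rule for an n other than 34 or 23. The consequence is conditional: it arises if cohorts close at enrolled, some patients have no scan, and the counts stay fixed.

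Under those conditions, with counts of 30 and 16, one lost patient costs about 17 points of HPV-positive power (75% to 58%) and 10 points of HPV-negative power (80% to 70%). At an assumed 5% loss unrelated to response, the average difference between fixed and realised-n cut-offs is 25 points (44% against 69%) and about 6 to 7 points (67% against 73%). The realised-n figures assume that unscanned patients leave the denominator. If they are kept as failures, that gain is not available and the remedy lies in the number enrolled.

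This should be fixed before the final analysis. It does not show that the plan rules out success.

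**What to change.** 1. Use one basis, enrolled or evaluable, for 57, 34 and 23 in sections 1.0, 2.1, 5.1.1, 5.5, 8.1 and 8.4.7, and align section 5.10 with it. Section 8.4.7 still mentions 39 evaluable patients. If the basis is evaluable, state the enrolment allowance. At an assumed 5% loss, 34/0.95 and 23/0.95 round up to 36 and 25.
2. State the primary denominator. Reconcile the scan requirement in section 8.4.2.2 with the non-responder rule in Table 7, so that patients lost to toxicity or death before day 150 do not drop out of it unnoticed.
3. In section 8.4.7.3 and Table 7, define success in each cohort as an exact one-sided binomial P of at most 0.05, against 74% or 50%, at the number analysed. Print the cut-offs:
   - HPV-positive: 34:30, 33:29, 32:29, 31:28, 30:27.
   - HPV-negative: 23:16, 22:16, 21:15, 20:15, 19:14.
4. Say openly that this replaces the asymptotic test.

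Cost: wording and one small table, and cut-offs one response higher than the asymptotic test at some n. No extra patients are needed unless the sponsor chooses the evaluable basis.
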